8.1.3 Exploratory study endpoints

Exploratory endpoints are defined as:

- The change in RFR, FFR, Pd/Pa, IMR and CFR over time after CTO PCI in a subset of patients undergoing repeated physiologic assessment during a staged procedure

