5. STUDY DESIGN

ULTRA-CTO is a prospective multicentre non-randomised investigator-initiated trial designed to enrol 200 subjects with an indication for PCI CTO.

After angiographically successful CTO PCI, intra-coronary physiologic assessment (RFR, FFR, CFR and IMR) and subsequent OCT of the CTO vessel will be performed. OCT may also be performed during a staged procedure when indicated (i.e. high contrast use, procedural duration, major dissection or other safety reasons according to the operator)..

[figure not shown]
When intra-coronary physiologic assessment or OCT is not possible at all, the patients will not be included in the study (6.1).

When the operator decides to optimize the stent result (post-dilation or additional stenting), based on the OCT and/or physiology, post-PCI RFR and FFR should be repeated.

For patients with a remaining intermediate stenosis (angiographically 30-90%) in a non-CTO vessel or major side branch of the CTO vessel with diameter ≥ 2 mm, clinically indicated FFR guided PCI will be planned within 4 ± 2 weeks. During this staged procedure, intra-coronary physiologic assessment (RFR, FFR, CFR and IMR) will be repeated in the CTO vessel for exploratory objectives (before additional PCI).

At 4 ± 2 weeks follow-up, the occurrence of cardiovascular events and clinical classification will be assessed for secondary objectives. See figure 2 for the study flow chart. A description of the primary and secondary endpoint(s) is included in paragraph 8.1.

Figure 2. Flowchart ULTRA-CTO

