7.1.1 Index procedure

1. After angiographically successful PCI of the CTO target vessel (no remaining lesion proximal or in-stent $\geq 30\%$, confirmed in two orthogonal projections with an angle ≥ 25 degrees apart), physiologic measurements must be performed in this vessel before additional OCT.

2. Physiologic assessment
 - Physiologic measurements must be performed using the Coroflow system (Coroventis) in combination with the PressureWire X (Abbott).
 - Physiologic measurements must be performed using intravenous adenosine and in the following order:
 - 1) Ensure adequate guide catheter position and adequate proximal venous access
 - 2) Administration of intracoronary nitrate (100 or 200 mcg)
 - 3) **RFR** 10 mm *proximal* to proximal stent edge.
 - 4) **Pd/Pa** (proximal arterial pressure/proximal aortic pressure without adenosine)
 - 5) **RFR** 10 mm *distal* to distal stent edge (without adenosine)
 - 6) **Pd/Pa** (distal arterial pressure/proximal aortic pressure without adenosine)
 - 7) Go to **CFR/IMR** mode: follow the steps and potential troubleshooting steps as indicated by the Coroventis software
 - Obtain the required hyperemia by infusion of intravenous adenosine with a dosage of 140 mcg/kg/min
 - **CFR** and **IMR** are calculated automatically.
 - Maintain hyperemia by continuing the infusion of adenosine
 - 8) Go to **FFR mode**:

- 10 mm *distal* to distal stent edge: FFR measurement after 20 heart beats during stable maximal hyperemia
- 10 mm *proximal* to proximal stent edge: FFR measurement after 20 heart beats during stable maximal hyperemia
- Stop infusion of adenosine
- **Check drift:** if drift >0.03 repeat physiologic measurements (description "drift")
- Additional OCT will be performed during the index procedure or staged when indicated..

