3. OCT

- OCT imaging of the stented segment in the CTO target vessel; starting and visualizing 10 mm distal from the stent edge and ending/visualizing 10 mm proximal of the stent edge.
- Based on the OCT findings and/or physiologic assessment, stent optimization (postdilation or additional stent placement) to eliminate treatable components of SSR (as defined in appendix I) is left to the operator's discretion.
- Distal RFR and distal FFR should be repeated after stent optimization
- It must be noted on the designated form which component(s) of SSR were seen and treated by the operator.
- In case the operator decides to perform one or more additional interventions or decides to refrain from additional interventions, it will be noted on the designated form what motivated the operator to do so
- End of procedure.

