7.1.2 Staged procedure (within 4 ± 2 weeks)

- 1) OCT may be performed during a staged procedure when indicated (i.e. high contrast use, procedural duration, major dissection or other safety reasons according to the operator). See details for OCT at 7.1.1, section 3.
- 2) For patients with a remaining intermediate stenosis (angiographically 30-90%) in a non-CTO vessel or major side branch of the CTO vessel with diameter $\geq 2\text{mm}$, clinically indicated FFR guided PCI will be planned within 4 ± 2 weeks. During this staged procedure, intra-coronary physiologic assessment (RFR, FFR, CFR and IMR) will be repeated in the CTO vessel for exploratory objectives (before additional PCI).
- 3) When the operator decides to optimize the CTO stent result (post-dilation or additional stenting), post-PCI RFR and FFR should be repeated.

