10.3 Analysis of secondary outcomes

Pearson r correlation and Spearman correlation coefficient rho (r) will be used to evaluate the degree of relationship between variables. For normally distributed variables, we will use the Pearson r correlation, while in case of skewed, ordinal data, the degree of association between variables will be quantified using Spearman correlation coefficient rho (r).

For repeated measurements (RFR, FFR, and other physiological parameters) we will use the paired t test for normally distributed variables and the Wilcoxon signed-rank test for skewed continuous data.

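### In patients whose stent is optimised at index, the planned change over time in CFR and IMR starts from a pre-optimisation value and so mixes the optimisation effect with time

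*Protocol*

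**What the plan says.** - **Index measurement.** Protocol 7.1.1 lists RFR, Pd/Pa, CFR, IMR and FFR after angiographic success and states that "physiologic measurements must be performed in this vessel before additional OCT".
- **Optimisation at index.** Under the OCT heading of 7.1.1, post-dilation or additional stenting "is left to the operator's discretion". A form records which components of suboptimal stent result were seen and treated, and why the operator did or did not intervene further.
- **Repeat after optimisation.** The same heading says "Distal RFR and distal FFR should be repeated after stent optimization". Section 5 agrees on which indices: "based on the OCT and/or physiology, post-PCI RFR and FFR should be repeated". Neither names CFR, IMR or Pd/Pa.
- **Staged measurement.** Sections 5 and 7.1.2 schedule RFR, FFR, CFR and IMR again in the CTO vessel at 4 ± 2 weeks, ahead of any further PCI. Pd/Pa is not in that list.
- **Endpoint.** Section 8.1.3: "The change in RFR, FFR, Pd/Pa, IMR and CFR over time after CTO PCI", in the subset whose physiology is measured again at a staged procedure.
- **Test.** Section 10.3: "For repeated measurements (RFR, FFR, and other physiological parameters) we will use the paired t test for normally distributed variables", with the Wilcoxon signed-rank test for skewed data. It does not say which index value is the baseline, and it does not set apart patients optimised at index.

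**The concern.** A paired change over time is interpretable only if nothing was done to the vessel between the two measurements. In a patient optimised at index, the treated vessel is altered after the only planned CFR and IMR reading. The staged reading then reflects both the extra intervention and the passage of time, and these data cannot separate the two.

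This matters for what the study wants to learn. Section 3 asks whether recovery after CTO PCI is microvascular or comes from enlargement of the distal lumen, and notes that an earlier study of CFR lacked a microvascular resistance measure such as IMR. CFR and IMR are thus the indices meant to inform that question, and they are the ones without a clean baseline in optimised patients. A procedural effect could be reported as recovery, or could mask it. The five indices would also not share a common starting point.

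**Working it through.** **Plan's own figure.** The protocol states no number for this endpoint. Its one computed figure, the primary sample size in 6.4, does not enter here. It does reproduce: a paired-AUC non-inferiority calculation with the Obuchowski variance, both AUCs 0.90, margin 0.10, one-sided 5%, 80% power, 40% prevalence and an assumed between-test correlation of 0 gives 190, and 190/0.95 = 200.

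**Step 1: which values are planned for a patient optimised at index and measured again at the staged procedure**

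| Parameter | Index, before optimisation | Index, after optimisation | Staged |
|---|---|---|---|
| RFR, FFR | yes | yes (distal) | yes |
| CFR, IMR | yes | no | yes |
| Pd/Pa | yes | not planned; possibly derivable from the stored resting recording | not named in 7.1.2 |

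**Step 2: what the paired difference estimates.** Let T be the true mean change over time, p the share of the repeat subset optimised at index, and d the mean immediate effect of optimisation on the parameter. With the pre-optimisation baseline,

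expected mean change = T + p × d.

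The bias p × d is zero if no one is optimised, if a post-optimisation baseline is used, or if the analysis is limited to patients not optimised. Patients optimised only at the staged procedure do not contribute, because their repeat physiology is taken first.

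**Step 3: scale for CFR.** Section 3 cites a rise in CFR from 2.01 (SD 0.58) to 2.50 (SD 0.79), so 2.50 − 2.01 = 0.49. That was at 5 months with a Doppler wire, so it serves only as a yardstick. Everything else here is assumed: p from 20% to 60%, d from 0.1 to 0.5 CFR units, subset size from 30 to 100, within-patient correlation 0.5, and a two-sided 5% test. The SD of the difference is

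√(0.58² + 0.79² − 2 × 0.5 × 0.58 × 0.79) = √0.5023 = 0.71.

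Simulated paired t tests (10,000 per setting) with T = 0 give:

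| p | d | Bias p × d | Share of 0.49 | Rejection at n = 30 / 60 / 100 |
|---|---|---|---|---|
| 0% | any | 0 | 0% | about 5% throughout |
| 20% | 0.1 | 0.02 | 4% | 5% / 6% / 6% |
| 40% | 0.3 | 0.12 | 24% | 14% / 24% / 37% |
| 60% | 0.5 | 0.30 | 61% | 56% / 87% / 98% |

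The sign of d is also an assumption. The protocol does not say in which direction optimisation would move CFR or IMR, and no comparable yardstick is given for IMR.

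**The case against.** The strongest reply is that this belongs in the statistical analysis plan. Section 10 defers technical detail to that document, section 10.3 only names tests, and the form in 7.1.1 already records what is needed to split patients by optimisation. Section 7.1 also refers to a more detailed operating procedure that is not shown. Part of this stands: the analysis plan could impose the split without loss. But the protocol itself fixes the measurement schedule, the parameters, the subset and the test, and as written these do not fit together for CFR and IMR in optimised patients. No later plan can recover CFR or IMR values that were never collected.

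Three further objections stand and limit the point.

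- **RFR and FFR.** A reader might infer that FFR recovery is swamped too. Scaling the cited +0.07 over 4 months linearly gives 0.07/4 = 0.0175 over 4 weeks. An assumed 20–50% optimised with a gain of 0.02–0.05 gives a bias of 0.004–0.025, or 23–143% of it. The documents do not support that reading: distal RFR and FFR are repeated after optimisation, so the bias arises only if the first value is chosen as baseline, which the protocol nowhere says. Nor does the figure measure the CFR and IMR problem.
- **Pd/Pa.** It is a resting pressure ratio, and section 7.2 requires raw recordings to be stored. A post-optimisation value may be obtainable, although none is planned.
- **Scope.** Only patients optimised at index who also return for staged physiology are affected. Inclusion requires a result that the operator already regards as final, and the endpoint carries no power statement or decision rule.

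**Conclusion.** The point holds for CFR and IMR in patients optimised at the index procedure, and for Pd/Pa if no post-optimisation value can be derived. For them, the paired change taken over all patients with repeat physiology mixes the optimisation effect with change over time.

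The size cannot be determined from the protocol, which states neither the size of the repeat subset nor the share optimised. The 40% prevalence of suboptimal stent result assumed in 6.4 is not that share, since treating the findings is optional. The CFR scenarios run from negligible (bias 0.02, rejection 5–6%) to serious (bias 0.30, rejection 56–98%) and rest on assumed values of p, d, subset size and correlation.

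It would be wrong to conclude that all five indices are compromised or that the main result is at risk. The primary comparison of AUCs and its sample size are unaffected. This is a cheap improvement to an exploratory analysis.

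**What to change.** Add to 8.1.3 and 10.3:

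1. The baseline for change in RFR and FFR is the last distal index value, taken after any optimisation.
2. Change in CFR and IMR is analysed in patients without stent optimisation at the index procedure. The same applies to Pd/Pa if no post-optimisation value can be derived from the stored recordings.
3. Optimised patients are shown separately for these parameters, described as change including the effect of optimisation.

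Section 7.1.2 should also be aligned with 8.1.3 on whether Pd/Pa is among the staged measurements.

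The addition is a few sentences and uses information already recorded on the 7.1.1 form. It needs no extra measurement and changes nothing in patient care. The downside is a smaller sample for two or three exploratory parameters, and results for them that describe only patients who were not optimised at index.

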8.2 Randomisation, blinding and treatment allocation

There will be no randomisation and thus no blinding of the randomisation assignment.

8.3 Study procedures

The following study phases and procedures can be distinguished. See figure 3 for a schematic overview of all study procedures.

8.3.1 Baseline (pre procedure)

Screening of eligible patients will be performed by the researchers. Eligible patients meeting the inclusion criteria will be asked for informed consent by one of the researchers. The operator will be informed about participation in the trial.

Accordingly the following baseline characteristics will be obtained before start of the procedure: patient characteristics, medical history, risk factors, blood sampling (creatinine clearance), the indication for the CTO PCI and specific characteristics of the CTO.

8.3.2 Index Procedure

Several variables regarding procedure-related technical characteristics and the study-related measurements will be collected during the index procedure.

8.3.3 Discharge

Occurrence of (S)AEs including MACE and other complications will be registered at discharge.

8.3.1 Staged procedure

At 4 weeks, prior to the staged procedure, clinical classification, occurrence of (S)AEs including MACE and other events will be registered.

Similar to the index procedure, several variables regarding procedure-related technical characteristics and the study-related physiologic measurements will be collected during the staged procedure.

Study procedure	Baseline (pre procedure)	Index procedure / hospitalization	Staged procedure (subset of patients)	Follow-up 4 ± 2 weeks
Patient eligibility: Inclusion/exclusion	X ¹			
Patient informed consent	X ²			
Baseline characteristics: - Patient characteristics - Blood sample (creatinine clearance) - Use of medication - Medical history - Risk factors - Indication for CTO PCI - CTO characteristics	X X ³ X X X X			
PCI procedure variables - Technical characteristics - Physiology parameters - OCT		X X X	(X) (X) (X)	
Clinical classification⁴	X			X
Adverse events and complications		X	(X)	X

Figure 3. Study procedures

1. This study will be conducted in subjects fulfilling all inclusion criteria and none of the exclusion criteria (see paragraph 6.1 and 6.2).
2. Written informed consent will be obtained before enrollment in the trial.
3. Blood sampling (creatinine clearance) will be performed according to standard care. No more than 20 ml of blood will be obtained during each sample.
4. CCS classification, NYHA classification and at staged procedure also SAQ score, TLR, ST, MACE, TVF.

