8.1.2 Secondary study endpoints (definitions in appendix I)

Secondary endpoints are defined as :

- The predictive value of the RFR and FFR gradient across the stented segment with regard to SSR in CTO patients.
- The correlation between positive RFR (≤ 0.89) and positive FFR (≤ 0.80) with regard to SSR following angiographically satisfactory CTO PCI.
- The correlation between post-PCI physiology (RFR, FFR, CFR, IMR) and SSR with anginal complaints (SAQ score), NYHA and CCS classification and MACE at follow-up.

- The correlation between OCT and/or physiology findings and physician-decision making (perform or refrain from additional PCI)

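### The protocol contradicts itself on who completes the Seattle Angina Questionnaire: only patients with a staged procedure, or everyone at the 4 ± 2 week follow-up

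*Protocol*

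**What the plan says.** Two places define what clinical classification contains, in identical words: footnote 4 to Figure 3 (section 8.3) and Appendix I. Both read "CCS classification, NYHA classification and at staged procedure also SAQ score, TLR, ST, MACE, TVF". The corresponding Figure 3 column heading begins "Staged procedure (subset of patients", so this visit does not apply to everyone.

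Other places put the assessment at follow-up without a subset limit:

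- Section 5: "At 4 ± 2 weeks follow-up, the occurrence of cardiovascular events and clinical classification will be assessed for secondary objectives".
- Section 8.1.2, which correlates post-PCI physiology and "SSR with anginal complaints (SAQ score), NYHA and CCS classification and MACE at follow-up".
- The Figure 3 row for clinical classification, marked at baseline and at the 4 ± 2 week follow-up, with nothing in the staged-procedure column.

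Section 8.3 has subsections for baseline, index procedure, discharge and staged procedure, but none for the follow-up visit. Its only text on the 4-week assessment sits under the staged procedure: "At 4 weeks, prior to the staged procedure, clinical classification, occurrence of (S)AEs including MACE and other events will be registered".

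A patient reaches a staged procedure by one of two routes. Section 5 names the first: "For patients with a remaining intermediate stenosis (angiographically 30-90%) in a non-CTO vessel or major side branch of the CTO vessel". Section 7.1.2 adds the second: "OCT may be performed during a staged procedure when indicated".

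No section schedules a baseline SAQ. The baseline list in section 8.3.1 is "patient characteristics, medical history, risk factors, blood sampling (creatinine clearance), the indication for the CTO PCI and specific characteristics of the CTO", and footnote 4 leaves only CCS and NYHA behind the baseline tick.

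**The concern.** The SAQ is the named measure of angina in a secondary endpoint, and the protocol gives two incompatible answers on who completes it and at which contact. This is a matter of data collection, so it cannot be left to the SAP: a questionnaire never handed out cannot be recovered at analysis.

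Under the footnote's reading, the angina correlation would rest on a subset of unstated size, and not a random one. Many in it would have a residual 30-90% stenosis outside the stented CTO segment. Their symptoms may reflect that disease, whereas the endpoint concerns the stent result and physiology in the CTO vessel. Such patients are in the full cohort too, but the restrictive reading concentrates them.

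**Working it through.** **Setting the texts side by side**

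| Place in protocol | SAQ or clinical classification collected at | Limited to a subset? |
|---|---|---|
| Figure 3, footnote 4 | Staged procedure (SAQ) | Yes |
| Appendix I, clinical classification | Staged procedure (SAQ) | Yes |
| Figure 3, grid row | Baseline and follow-up; staged cell blank | No |
| Section 5 | Follow-up (SAQ not named) | No |
| Section 8.1.2 | Follow-up (SAQ named) | No |
| Section 8.3, staged procedure text | Before the staged procedure | Yes, by its position |

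1. The one visit at which the footnote adds the SAQ is a visit the grid leaves unmarked for that row. The adverse-event row just below does carry a mark in the staged column, so the blank is probably real and not an extraction fault.
2. Section 5 and the grid do not resolve the conflict, because both use clinical classification, the term that Appendix I defines with the restriction. Only section 8.1.2 names the SAQ directly at follow-up.
3. Staged procedure cannot simply be read as the 4-week visit. Section 9.2.1 treats follow-up and the staged procedure (in a subset) as alternative end points for recording adverse events.
4. Where the protocol means a subset it says so: section 3 (end), section 4.3 and section 8.1.3 do this for repeated physiology. The SAQ objective (4.2) and endpoint (8.1.2) carry no such limit.

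Steps 1 and 4 indicate that follow-up for all is the likely intent and that footnote 4 and Appendix I are the wrong text.

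**What the restrictive reading would cost in precision**

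The protocol gives no power figure for this endpoint, so there is none to reproduce. Inputs: 190 patients (section 6.4, before the increase to 200 for dropout); two-sided 5% and 80% power, assumed here; staged shares of 50%, 30% and 20%, also assumed because the protocol states none.

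By the Fisher z approximation, the smallest detectable correlation is r = tanh[(1.960 + 0.842)/√(n − 3)] = tanh[2.802/√(n − 3)].

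| Share with SAQ | n | 2.802/√(n − 3) | Detectable r |
|---|---|---|---|
| 100% | 190 | 2.802/√187 = 0.205 | 0.20 |
| 50% | 190 × 0.50 = 95 | 2.802/√92 = 0.292 | 0.28 |
| 30% | 190 × 0.30 = 57 | 2.802/√54 = 0.381 | 0.36 |
| 20% | 190 × 0.20 = 38 | 2.802/√35 = 0.474 | 0.44 |

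**The case against.** The strongest reply is that nobody would read the footnote restrictively. Section 4.2 lists the SAQ among the secondary objectives, section 5 says follow-up data serve those objectives, and section 8.1.2 places the SAQ at follow-up. The footnote also bundles the SAQ with MACE, which is plainly a follow-up endpoint for all. On this view, the staged-procedure wording is loose shorthand for the 4-week contact. This shows what was probably intended, but it does not make the footnote or the definition correct. It also protects MACE better than the SAQ: section 5 and the adverse-event row record events at follow-up by a second route, and the SAQ has none.

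Second, part of the evidence is out of sight. Figure 2 is not shown, the extracted Figure 3 is imperfect (seven baseline items but six marks), and the eCRF may already open the SAQ for everyone. Data loss is therefore a risk and not an established fact. The conflict between the footnote and section 8.1.2 does not depend on any of these.

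Third, the precision figures are illustrative. The staged shares are assumed, 190 is the sample size for the AUC comparison, SSR is binary, and section 10.3 uses Spearman for skewed or ordinal data. That stands: the figures show a scale, not a forecast.

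Fourth, the endpoint is a correlation with follow-up SAQ, not a change from baseline, so a baseline SAQ is not required. Its absence from the section 8.3.1 list is also weak evidence, since that list omits CCS, NYHA and medication use, which Figure 3 does schedule. That stands too, and a baseline SAQ is only an option.

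**Conclusion.** The contradiction is in the text. Footnote 4 and Appendix I tie the SAQ to a subset visit, while section 8.1.2 places it at follow-up without a subset limit. Because staged procedure and follow-up share the 4 ± 2 week window, the dispute is mainly about who completes the SAQ and at which contact, less about calendar time.

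The harm is conditional on sites following the footnote. In that case, patients without a staged procedure contribute nothing to the angina correlation. With an assumed staged share of 20-50%, the detectable correlation worsens from 0.20 to 0.28-0.44, in a selected group. CCS and NYHA are still collected, and the primary comparison of RFR and FFR is untouched. The point should be corrected because the fix is cheap and missing questionnaires cannot be recovered. Confidence is high on the contradiction itself; whether data would actually be lost depends on site practice and the eCRF, which the protocol does not show.

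**What to change.** - Amend footnote 4, the Appendix I definition and, where needed, the Figure 3 grid so that every patient completes the SAQ at the 4 ± 2 week follow-up. For patients with a staged procedure, this is before that procedure, as section 8.3 already has it for clinical classification.
- Align the footnote's wording on TLR, ST, MACE and TVF with the event recording at follow-up in section 5, section 8.1.2 and the adverse-event row of Figure 3.
- Add a short follow-up visit subsection to 8.3 listing these items.
- Optionally, collect the SAQ at baseline so that follow-up scores can be adjusted for it. The choice of covariates can stay with the SAP announced in section 10.

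The cost is wording changes, the short subsection, and one questionnaire at an existing contact for patients without a staged procedure. The optional baseline SAQ adds one more questionnaire at an existing contact. For patients already enrolled, baseline CCS and NYHA remain available.
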